Secondary clinical and functional measures will come from the Patient-Reported Outcomes Measurement Information System Adult Profile (PROMIS 29+2). It includes measures of Physical Function, Social Roles, Anxiety, Depression, Fatigue, Sleep Disturbance, Pain Interference, Pain Intensity, and Cognitive Function. Each construct is scored individually (4 items, range 4-20) except Cognitive Function (2 items, range 2-10), with higher scores indicating more of the construct being measured. Raw scores are translated to a T-score with a mean of 50 and SD of 10. When all constructs are scored together, a preference score is calculated, representing health-related quality of life ranging from 0 (as bad as dead) to 1 (perfect or ideal health).⁶²

Screening

- Via phone or video telehealth (e.g., MS Teams, VVC) to confirm inclusion/exclusion criteria

Inclusion Criteria

- VAPHS Veterans ≥ 18 years
- Medical record documentation and self-report of active sedative-hypnotic use ≥ 3 days/week for ≥ 3 months: z-drugs (zolpidem: ≤ 10 mg IR, ≤ 12.5 SR; zaleplon: ≤ 20 mg; eszopiclone: ≤ 3 mg); trazodone (≤ 400 mg); temazepam (≤ 30 mg); hydroxyzine (≤ 100 mg); Veterans on higher doses may be eligible on a case-by-case basis
- A desire to reduce or stop using sedative-hypnotics
- Access to a mobile device

Exclusion Criteria

- A self-report of a medical and/or psychiatric disorder that would significantly impair participation (e.g., cancer, uncontrolled pain, severe depression)
- A self-report of a medical and/or psychiatric disorder that can be exacerbated by changes in sleep (e.g., seizure disorder, psychotic disorders, bipolar I disorder)
- A self-report of an active substance use disorder
- High risk of suicide per the Columbia-Suicide Severity Rating Scale (C-SSRS)
- Currently engaged in an evidence-based, time limited, psychotherapy (e.g., prolonged exposure, cognitive processing therapy, cognitive behavioral therapy for depression, cognitive behavioral therapy for insomnia, etc.)

Interventions

Pharmacist-led Deprescribing

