CBT-I risk. CBT-I is an evidence-based, multi-component psychotherapy regularly delivered within the VHA. CBT-I is the recommended first line treatment for insomnia per the VA/DOD Clinical Practice Guidelines, the American Academy of Sleep Medicine, and the American College of Physicians among other professional societies.^{12,25,40} Furthermore, there are several online and/or mobile app-based, self-management CBT-I interventions that have good evidence to improve symptoms with similar outcomes as in-person treatment.³ The CBT-I intervention delivered through COAST uses proprietary algorithms to develop personalized recommendations based on the patient-reported data from users. COAST treatment recommendations are always reviewed by providers prior to being delivered to the participant. For this study, [name] (PI), a licensed psychologist with expertise in insomnia/behavioral sleep medicine, will review all COAST treatment recommendations prior to their delivery to participants and make changes based on clinical expertise and knowledge of each participant as needed.

Suicide risk. Regarding suicidal ideation/behaviors, Veterans who are at high risk per the Columbia-Suicide Severity Rating Scale (C-SSRS) will be excluded and referred to the

appropriate resources following VAPHS guidelines. Specifically, Veterans with active suicidal ideation with intent and/or plan will be excluded. Veterans with ideation but no current intent or plan, but with a history of suicide attempts (including preparing for, interrupted, or aborted attempts) or self-injury in the past year will also be excluded. For Veterans who are eligible, those with suicidal ideation without method, plan, or intent will be monitored weekly with the C-SSRS through the COAST platform. If a Veteran meets elevated criteria for suicide risk (e.g., ideation with intent, plan, behaviors), they will be withdrawn from the study and referred for appropriate care per VAPHS guidelines.

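### As written, suicidal ideation with a method but no plan, intent or relevant history is neither expressly excluded nor given the weekly C-SSRS

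*Combined protocol and SAP*

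**What the plan says.** All the rules sit in the Suicide risk paragraph of Section 5.1 (Risks and Benefits). It first restates the general exclusion for high risk on the C-SSRS, then gives its content:

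- First exclusion: "Specifically, Veterans with active suicidal ideation with intent and/or plan will be excluded".
- Second exclusion: "Veterans with ideation but no current intent or plan, but with a history of suicide attempts" (preparatory, interrupted and aborted attempts count) "or self-injury in the past year will also be excluded".
- Monitoring, for Veterans found eligible: "those with suicidal ideation without method, plan, or intent will be monitored weekly with the C-SSRS through the COAST platform".
- On-study withdrawal: "If a Veteran meets elevated criteria for suicide risk (e.g., ideation with intent, plan, behaviors), they will be withdrawn from the study", with referral for care.

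The exclusion lists in Sections 5.1 and 5.2 repeat the general high-risk criterion without a score or item cut-off. No other section schedules a C-SSRS during the intervention.

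**The concern.** The monitoring sentence lists method separately from plan, so the authors appear to treat them as different things. Method appears in neither exclusion sentence and is not among the withdrawal examples. A Veteran with ideation and a method, but no plan, intent, attempt history or past-year self-injury, therefore passes both written exclusions and falls outside the written monitoring group.

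Followed literally, the scheduled suicide assessment goes to the less specific ideation and not to the more specific. This happens during a remotely managed hypnotic taper in which the protocol expects rebound insomnia (Section 5.1, Deprescribing/withdrawal risk), and the protocol's own background links insomnia to suicide behaviors (Section 2.0). Withdrawal for elevated risk depends on detecting it. Between baseline and post-treatment, staff would learn of a change in this Veteran only through general channels.

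The same gap can open on study. A participant who enters with ideation alone and later reports a method meets none of the named withdrawal examples, and no action is stated.

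**Working it through.** The plan states no figure on this point. The check is whether the written rules cover every case.

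**Inputs.** Given that ideation is present, take four yes/no features from the Suicide risk paragraph: method (m), plan (p), intent (i), and history (h: an attempt, or self-injury in the past year). This gives 2^4 = 16 combinations.

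**Applying the rules in order.**

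| Rule | Condition | Combinations |
|---|---|---|
| First exclusion | p = 1 or i = 1 | 16 − 4 = 12 |
| Second exclusion | p = i = 0, h = 1 | 2 |
| Weekly C-SSRS | m = p = i = h = 0 | 1 |
| Not named | m = 1, p = i = h = 0 | 1 |

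Expressly excluded: 12 + 2 = 14. Total: 14 + 1 + 1 = 16.

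**Sensitivity to coding.** Splitting history into attempt and self-injury gives 2^5 = 32 combinations: 24 excluded for plan or intent, 6 excluded for history, 1 monitored, 1 not named. The unnamed case is the same one. The count above reads the one-year limit as applying only to self-injury. If it also limits attempts, a Veteran with a method and an older attempt joins the gap.

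**Scheduled assessments for the two remaining cases.**

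- Weekly C-SSRS, ideation without method: 12 weeks × 1 = up to 12. This assumes monitoring lasts for the whole intervention of up to 12 weeks; the paragraph gives no end point.
- Weekly C-SSRS, method only: 0 stated.
- PROMIS Depression, both cases: baseline, post-treatment and 3 months later = 3 time points, with 0 between baseline and post-treatment.

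**Other safeguards for the method-only Veteran.** Self-reported severe depression that would significantly impair participation is an exclusion, as is severe or unstable psychiatric illness (Section 5.2). A daily question on unexpected symptoms leads, if positive, to the CIWA-B, a withdrawal scale, with review on weekdays. A clinician approves each COAST recommendation and can be messaged, and crisis line details are provided. The protocol describes none of these as a scheduled suicide assessment.

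**After the fix.** If method remains eligible: 14 excluded and 2 monitored. If method is named as high risk: 15 excluded and 1 monitored. Either way 0 are unnamed.

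**The case against.** The strongest reply is that the monitoring sentence can be read as describing which Veterans with ideation remain eligible. Plan and intent have already been excluded by that point, so repeating them removes nobody new. Method may be doing the same work, on the understanding that a Veteran with a method is high risk and is not enrolled. The general C-SSRS criterion and the open-ended withdrawal examples allow that reading. The C-SSRS scoring and the site's guidelines, which might settle it, are not reproduced in the protocol.

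This reading is possible, but the text does not establish it. The exclusions are introduced as the specific content of high risk, and method is not among them. Either intention needs an edit: if method is high risk, the exclusion and withdrawal sentences omit it; if it is eligible, the monitoring sentence omits it.

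It is also fair to say that the combination counts depend on how the features are coded, that they assume the features vary freely, and that combinations are not Veterans. The counts show where the gap lies, not how often it would occur. The general surveillance is also more active than a single symptom question: psychological discomfort is assessed daily, reports of distress lead to contact from the pharmacist or psychologists, and the withdrawal rule applies to any Veteran. That lowers the risk but does not supply a scheduled suicide assessment.

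**Conclusion.** The concern holds as a gap in the written rule. Exactly one configuration, ideation with a method and nothing else, has no stated handling: up to 12 scheduled C-SSRS assessments for the less specific ideation against none for this one. It is probably a drafting slip. It does not show that such a Veteran would be enrolled or that the sponsor meant to monitor lower risk in preference to higher.

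The conclusion rests on a literal reading in which method and plan are distinct, as the monitoring sentence implies. The number of Veterans affected cannot be derived from the protocol and may be zero. Sample size, power and the analyses in Section 5.3 are untouched. The change is worth making because it bears on participant safety and costs almost nothing.

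**What to change.** Reword the monitoring sentence in the Suicide risk paragraph of Section 5.1 along these lines: *every eligible Veteran with any suicidal ideation will complete the C-SSRS weekly through COAST*. This works whether or not method is an exclusion, because it applies only to those found eligible.

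Two minor clarifications could go in at the same time:

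- State whether ideation with a method counts as high risk. If it does, name it in both the exclusion and the withdrawal sentences.
- Section 5.4 makes withdrawal for high suicide risk optional, whereas Section 5.1 makes it mandatory. Align Section 5.4 with Section 5.1.

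The cost is one changed sentence plus small editorial edits. The C-SSRS is already planned in COAST, so the added burden is up to 12 short questionnaires per affected Veteran, and none if no such Veteran enrolls.

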5.2 Study Population, Recruitment Methods, and Informed Consent Process

Study Population/Inclusion and Exclusion Criteria

Inclusion Criteria

- VAPHS Veterans ≥ 18 years
- Medical record documentation and self-report of active sedative-hypnotic use ≥ 3 days/week for ≥ 3 months: z-drugs (zolpidem: ≤ 10 mg IR, ≤ 12.5 SR; zaleplon: ≤ 20 mg; eszopiclone: ≤ 3 mg); trazodone (≤ 400 mg); temazepam (≤ 30 mg); hydroxyzine (≤ 100 mg); Veterans on higher doses may be eligible on a case-by-case basis
- A desire to reduce or stop using sedative-hypnotics
- Access to a mobile device

Exclusion Criteria

- A self-report of a medical and/or psychiatric disorder that would significantly impair participation (e.g., cancer, uncontrolled pain, severe depression)
- A self-report of a medical and/or psychiatric disorder that can be exacerbated by changes in sleep (e.g., seizure disorder, psychotic disorders, bipolar I disorder)
- A self-report of an active substance use disorder
- High risk of suicide per the Columbia-Suicide Severity Rating Scale (C-SSRS)
- Currently engaged in an evidence-based, time limited, psychotherapy (e.g., prolonged exposure, cognitive processing therapy, cognitive behavioral therapy for depression, cognitive behavioral therapy for insomnia, etc.)

Inclusion of Women, Minorities, and Children

Women and minorities will be included in this study. Children (i.e., under the age of 18) will not be enrolled in this study. Also, no prisoners or currently hospitalized Veterans will be enrolled. Veterans with severe and/or unstable medical/psychiatric illnesses will also be excluded from this study (see Inclusion/Exclusion Criteria above) as will Veterans at high risk for suicide. No exclusion criteria shall be based on race, ethnicity, gender, religion, or HIV status.

Master List

A master list of enrolled participants will be maintained. A Veteran is considered enrolled after completing the informed consent process. The master list will be stored on the secure VA study drive and only accessible by approved study staff.

Recruitment Methods

The goal is to recruit and enroll 50 Veterans from VAPHS and affiliated CBOCs. Rather than recruiting in clinic and in-person, as is common for intervention trials such as this, to expand the pool of eligible participants we will primarily recruit through mail. The study team will mail a letter (see Recruitment Letters) to potentially eligible Veterans, based on inclusion and exclusion criteria, utilizing data from Veteran medical records. These letters will be sent from service line leaders at VAPHS—Behavioral Health, Primary Care, and Medicine (representing Sleep Medicine). A pre-screen list of potentially eligible Veterans will be generated by the study's data analyst, through VA's Corporate Data Warehouse, and stratified by sex (male/female), race (White/non-White), and age (<65/≥65) as an attempt to recruit a diversified sample. Then, letters will be mailed weekly to potentially eligible Veterans randomly selected from each stratified group (e.g., ~20-25/group). Letters will be sent until the goal of 50 Veterans have been enrolled.

Letters will ask Veterans to call the study coordinator for more information or they can return a letter indicating their interest. Interested Veterans who contact the study team will then schedule an eligibility screen (e.g., phone, Teams, VVC) with the study coordinator.

If feasible, depending on COVID-19 restrictions, recruitment will take place in VAPHS clinics (e.g., Primary Care, Behavioral Health, Sleep Medicine) in addition to the mail recruitment campaign. This may involve clinicians describing the study to their patients and providing study contact information as well as IRB approved fliers posted through VAPHS.

	White		Non-White		Total
	<65	≥65	<65	≥65	
Female	82	24	29	2	137
Male	346	859	48	65	1318
Total	1311		144		1455

As part of the proposal, a preparatory to research data query found VAPHS has n=1,455 Veterans who used sedative-hypnotic medications >14 doses/month for ≥3 months from 01/01/2019 to 01/31/2021 without diagnoses that would exclude

them from participating. A new CDW query, using updated inclusion criteria, will update the pool of potential participants as of 1/31/2023. If feasible, depending on COVID-19 restrictions, recruitment will take place in VAPHS clinics (e.g., Primary Care, Behavioral Health, Sleep Medicine) in addition to the mail recruitment campaign. Clinicians familiar with the study can also notify the research team of interested, potentially-eligible participants via a research specific CPRS consult, so that a study member can contact a Veteran directly. This will minimize the burden on the clinician and help recruitment in clinical settings be more efficient.

Informed Consent Process

Interested Veterans who respond to the letter recruitment (or other methods) will be scheduled to undergo a screen (e.g., phone, Teams, VVC, in-person [only if necessary]) to confirm inclusion/exclusion criteria. The study team will also review their electronic medical record to confirm aspects of inclusion/exclusion criteria. If eligible, they will be invited to undergo the informed consent process via remote procedures (e.g., phone, Teams, VVC) or in-person if requested. For remote consent, Veterans will sign the ICF + HIPAA using DocuSign. If in-person, the Veteran will complete a written ICF + HIPAA.

Following consent, participants will be instructed on how to download the patient facing COAST app to their mobile device. Once downloaded, it will be activated with a unique code to prevent the app being used on another mobile device. Once the app is activated, the participants will be assigned a unique ID number, will undergo a brief training on how to use COAST, including instructions on how to access and navigate to the content areas, how to enter data for measures, how to use the sleep diary, and how to use the secure messaging. Previous testing of the COAST app by military Veterans and Service Members found its usability to be excellent and it received high scores for ease of use and learnability.⁵⁵ Since the initial development, the user interface has been further improved to meet the needs of users. Also, any technical issues with the app will be rapidly responded to by the study/Noctem team. After the app training, participants can then complete the baseline assessment in the COAST app.

5.3 Data Analysis

This study is focused on the feasibility of recruitment and participation, usability and acceptability of COAST, and estimates of change in Veteran sleep and sedative-hypnotic use. The findings from this SPiRE will inform the study design of a larger clinical trial (e.g., RR&D Merit). A meta-analysis of digital CBT-I (2016) found a hedge's g of 1.09 (95% CI 0.74-1.45) when evaluating pre-post change on the Insomnia Severity Index (or similar measures).⁵⁴ The only study, to date, using NOCTEM COAST found a pre-post Cohen d of 1.93 for the ISI.⁵⁶ While there are few studies specifically looking at CBT-I plus sleep medication deprescribing, they show large effect sizes for change on the ISI (Cohen d = 1.98-2.26).^{49,64,65} Given the estimates from prior work conducted, we can expect an effect size range for pre-post ISI between 1.09 and 2.26 with an average effect size of 1.73 (large effect sizes). Given 50 recruited and accounting for a 25% drop out (i.e., 37 completers), we will still have 95% power to be able to detect an effect size of 0.65.

Prior to analyses for each aim, participant characteristics will be evaluated with descriptive statistics (e.g., age, sex, race). Distributions will be examined for normality, outliers, and missing data. Continuous variables (means/SD) and categorical variables (frequency/percentage) will be reported.

Aim 1. Feasibility will be evaluated in two ways. The first is by participant recruitment—how many participants contact the coordinator, undergo the study screen, and provide consent. The second is by treatment participation—how many participants download and activate the COAST app, complete baseline assessments, engage in treatment beyond the initial recommendation, and complete the intervention. Chi-square analyses will be used to determine group differences (age, sex, race) in recruitment response and participation rates.

Aim 2. Usability and acceptability of COAST will be evaluated by the PSSUQ measure. Usability/acceptability will be measured early in treatment ($T_{0+1\text{-week}}$) and at post-treatment (T_1) as well as change over time ($T_1 - T_{0+1\text{-week}}$). Change will be assessed using an intent-to-treat (ITT) approach and fitting mixed effects linear models that tests change in usability/acceptability (change on PSSUQ scores over the course of treatment) that includes a main effect of time ($T_{0+1\text{-week}}$ to T_1) and random effects for the Veteran.

Audio-recorded qualitative interviews will help to gain more nuanced information on COAST usability/acceptability. The interviews will be interpreted using the rapid qualitative inquiry^{66,67} to ensure that results are delivered in a timely manner to be meaningful to the study. Interviews will be summarized by the study's qualitative analyst into a template of categories that reflect topics of interest. The summaries will be coded by two analysts to develop the basis of content and thematic analyses.

Aim 3. Veteran clinical and functional outcomes will be evaluated with an ITT approach. We will fit mixed effects linear models that test change pre-post treatment (ISI, sleep diary, PROMIS) that includes a main effect of time (T_0-T_1 , T_0-T_2 , and T_1-T_2) and includes random effects for the Veteran (multiple measurements during treatment). Sedative-hypnotic change will be a determined by an ITT approach and fitting a mixed methods logistic model that tests for dose reduction ($\geq 50\%$, yes/no) and cessation of medication (yes/no) over the

course of treatment that includes a main effect of time (T_0-T_1 , T_0-T_2 , and T_1-T_2) and random effects for the Veteran. Additional analyses will compare completers vs. non-completers and responders vs. non-responders.

The study data analyst/statistician will lead quantitative analyses and the study qualitative analyst will lead qualitative analyses. The PI and Co-Is will also be involved in study analyses and interpretation.

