5.0 Study Procedures

5.1 Study Design

Assessments

All patient-reported assessments will be conducted through the COAST platform. Additional data will be collected from participants' VA medical records (e.g., diagnoses, medications, service connection, service utilization). Assessments will occur at baseline ($T_0/ \sim T_{0+1\text{week}}$), post-treatment (T_1), and 3-months post-treatment (T_2) unless otherwise specified.

Study *feasibility* will be assessed by recruitment and intervention participation. Response to recruitment letters (# responses / # letters mailed) will be assessed overall and for each stratified group (age, sex, race). Participation will be assessed by number of enrolled participants that activate the COAST app, complete baseline assessments, engage in treatment beyond the initial recommendation, and complete the intervention.

COAST *usability* and *acceptability* will be measured with the Post-Study System Usability Questionnaire (PSSUQ).⁵⁹ The PSSUQ measures perceived satisfaction with a "system" like a website or mobile app. The PSSUQ is 16-items, scored 1-7 (1-strongly agree, 7-strongly disagree) or not applicable (N/A). The usability score is the average (total score divided by number of questions answered [N/A not included]). The three sub-scales are: usefulness (items 1-6), information quality (items 7-12), and interface quality (items 13-16). Lower scores, <3, indicate higher satisfaction and above average usability. The PSSUQ will be assessed at two time points. First, after the initial sleep/wake schedule recommendation is delivered ($\sim T_{0+1\text{ week}}$) as this will give participants a chance to learn the COAST platform and second, at T_1 , to measure change over time.

To further assess usability/acceptability, 15 Veterans will be interviewed (e.g., phone, Teams, VVC) to gain context on their COAST user experience and potential changes or new features that could improve COAST. Veterans will be interviewed based on their PSSUQ scores to get a range of perspectives, if available, per score distribution (e.g., 5 low, 5 medium, 5 high).

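### Aim 1's chi-square tests of age, sex and race differences (6 to 21 of them, none labelled exploratory) rest, for participation, on tables mostly too sparse for the method

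*Combined protocol and SAP*

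**What the plan says.** Section 5.3, Aim 1, evaluates feasibility in two ways. Recruitment is "how many participants contact the coordinator, undergo the study screen, and provide consent". Participation is "how many participants download and activate the COAST app, complete baseline assessments, engage in treatment beyond the initial recommendation, and complete the intervention". It then says: "Chi-square analyses will be used to determine group differences (age, sex, race) in recruitment response and participation rates".

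Section 5.1 defines the response measure more narrowly: "Response to recruitment letters (# responses / # letters mailed) will be assessed overall and for each stratified group (age, sex, race"). It counts participation among enrolled participants.

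Section 5.2 makes each factor binary, with the mailing list "stratified by sex (male/female), race (White/non-White), and age (<65/≥65) as an attempt to recruit a diversified sample". On size, "The goal is to recruit and enroll 50 Veterans from VAPHS and affiliated CBOCs", and section 5.3 adds "Given 50 recruited and accounting for a 25% drop out (i.e., 37 completers").

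The documents give no significance level, lead rate, multiplicity adjustment, small-sample alternative or exploratory label for these comparisons.

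**The concern.** Two things look wrong.

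- **Multiplicity.** An unspecified number of subgroup tests is run at an unspecified level, and the stated purpose is to determine differences. Because the count can be read as 6, 15 or 21, it could be settled after the data are seen.
- **Method.** The participation tests divide about 50 people by sex, race and age and compare steps at which few people fail. The chi-square approximation is weak there. A non-significant result would say little about equal participation, and an isolated significant one could be chance.

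Section 5.3 says the findings will inform the design of a larger trial, and mailing is stratified by these same three factors. A group difference reported as established, or a real one missed, could therefore colour that trial's recruitment plan.

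**Working it through.** **Plan's own figures.** 50 × 0.75 = 37.5, which the plan rounds down to 37 completers, leaving 50 − 37 = 13 non-completers. Aim 1 has no error rate or power figure to reproduce; the only power statement in 5.3 concerns pre-post change on the ISI.

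**Number of tests** (three binary factors, one degree of freedom each):
- every step in 5.3: (3 recruitment + 4 participation) × 3 = 21
- response as the single rate in 5.1, all four participation steps: (1 + 4) × 3 = 15
- one response rate and one participation rate: 2 × 3 = 6

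**Chance of at least one false difference.** The significance level is not stated; two-sided 5% is assumed. If tests were independent, 1 − 0.95^k gives 26.5% (k = 6), 53.7% (k = 15) and 65.9% (k = 21). The steps are nested, so the tests are correlated, and simulation is the better guide.

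Inputs from 5.2: the eight pool cells (82, 24, 29, 2, 346, 859, 48, 65), 22 letters per cell per week, and mailing until 50 consent or the pool is used up. Assumed: response of 5–25%, screening 80%, consent 75%, completion about 75%, and identical rates in every group. Denominators are letters mailed for recruitment and enrolled Veterans for participation.

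| Tests | Uncorrected Pearson | Continuity-corrected (response 10–25%) |
|---|---|---|
| 21 | about 45–51% | about 26–30% |
| 15 | 38–43% | about 19–23% |
| 6 | 23–27% | about 14–17% |

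Including 5% response, the corrected figures span about 12–30%. The denominators for screening and consent are not defined. If every step is instead divided by those who reached the previous step, the 21-test uncorrected figure is 55–65%, over wider assumptions about response and completion.

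**Sparsity from the plan's figures alone.** In a group of size g, the expected number of non-completers is g × 13/50. For g = 19 this is 4.94; for g = 20 it is 5.2. So any group under 20 falls below 5 at completion, the step with the most failures. At an earlier step with F failures among 50, even an even 25/25 split has an expected count of F/2, so F below 10 makes the table sparse for all three factors.

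Women are 137 of 1,455 in the pool (9.4%) and non-White Veterans 144 of 1,455 (9.9%). In the simulation, stratified mailing yields a median of 8, 12 and 18 women enrolled at 10%, 15% and 25% response. With 12 women, the expected number of female non-completers is 12 × 13/50 = 3.1. Across response rates of 5–25%, 81–98% of the participation tables have a minimum expected count below 5.

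**Detectable gap in completion by sex** (80% power, two-sided 5%, 75% completion), 2.8 × √[0.75 × 0.25 × (1/n₁ + 1/n₂)]:
- 8 v 42: 0.47
- 12 v 38: 0.40
- 18 v 32: 0.36

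That is about 35–47 percentage points.

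**Response per letter.** If the whole pool is mailed and response is only 5%, expected responders are 137 × 0.05 = 6.9 women and 144 × 0.05 = 7.2 non-White Veterans, both above 5. Chi-square is serviceable here.

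**The case against.** The strongest reply is that this is a single-arm feasibility pilot. H1 says only that recruitment will be feasible, and no hypothesis, threshold or go/no-go rule rests on a group difference. Response will in any case be reported by group (5.1), and categorical variables as frequencies and percentages (5.3). Family-wise control of secondary subgroup comparisons in such a study is a matter of convention. This stands, and it is why adjustment is not required.

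A reader might infer that a false difference is close to an even chance. The documents do not support that as a general statement. It needs all 21 tests and uncorrected Pearson chi-square at 5%, whereas 5.1 defines recruitment response as one rate, which makes 15 the best-supported count for the full funnel. It also takes uncorrected chi-square at face value on tables where it is unreliable.

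A reader might also infer that the next trial would be aimed at the wrong Veterans. The documents say only that findings will inform its design, and the benefits text in 5.1 foresees a diverse sample, which points away from narrowing by race, sex or age.

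Finally, sparsity is uneven. Enrolment by age is nearly balanced (about 24 v 28 in the simulation), and for completion by age only about a third of tables fall below 5 at response rates of 10–25%. The pool counts come from a query that 5.2 says will be updated, and possible clinic recruitment is not modelled. These limits qualify the percentages but not the 13/50 arithmetic.

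**Conclusion.** The point holds as a minor to moderate one. The firm part is the method: with about 50 enrolled and 13 expected non-completers, chi-square is unreliable for most participation tables, mainly sex and race at completion and nearly all tables at earlier steps. The tests could reveal only very large gaps.

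The multiplicity part is real but conditional. It depends on the assumed 5% level, on whether 6, 15 or 21 tests are meant, on the version of chi-square, and on the denominators. On every count examined the risk is at least double the nominal 5%.

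The general feasibility framing does not itself label these comparisons descriptive, and the verb *determine* points the other way. Nothing here undermines Aim 1's main feasibility counts.

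**What to change.** In 5.3, Aim 1:
- Report the four participation comparisons, and screening and consent if they are compared, as group rates and differences with 95% confidence intervals suited to small counts (Newcombe or exact), in place of chi-square p-values.
- Label these comparisons exploratory and replace *determine* with *describe*.
- Keep chi-square, if wanted, for response per letter by age, sex and race. Holm adjustment over those three tests is optional: unadjusted, three independent tests at 5% carry 1 − 0.95³ = 14.3%; under Holm the smallest p-value must be at most 0.05/3 = 0.0167.
- State the significance level for any test kept, and the denominator for each rate.

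The cost is a few sentences, with no new data or participants. The downside is that no significance claim can be made for the later funnel steps.
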